shoulder arthroscopy who receive post-operative CBD and a placebo group. Patients will be asked on postoperative Day 1, 2, 7, and 14 to rate their pain according to the VAS scale. Additionally, opioid consumption, CBD consumption, as well as patient satisfaction will be measured. Patients will be asked in the post-trial period to fill out a questionnaire pertaining to 1-year outcomes. The questionnaire will be in the form of a single online survey including ASES score, VAS score, KJOC Shoulder score, and SANE score.

Rationale for multi-center study:

The second site is essential for this project, for both recruitment and logistical purposes. While NYULOH does have high-volume, a large proportion of these patients will be ineligible due to the exclusion criteria and will not want to participate given that this is a randomized, controlled, double blinded study. Additionally, the second site PI was absolutely instrumental in the conceptualization and the design of this study, as well as securing the necessary funding for it happen. This study would not be feasible without their collaboration. Additionally, the second site PI has an academic appointment here at NYU Langone, and is instrumental in the education of the trainees here at our institution

Primary Objective

The primary objective of the study is to determine if there are any differences in post-operative pain between patients receiving CBD after shoulder arthroscopy compared to patients who do not receive it.

Secondary Objective

Secondary objective of the study is to determine if there are any differences in patient satisfaction, the incidence of opioid induced nausea, and the numbers of opioids and CBD/placebo ODTs consumed by the two patient cohorts.

II. CHARACTERISTICS OF THE RESEARCH POPULATION

Number of Subjects

We will aim to enroll a total of 100 subjects (50 per cohort) as determined by the priori sample size calculator.

Gender of Subjects

Men and women will be included in this study.

Age of Subjects

Subjects included study will be aged 18-75 years, inclusive.

Racial and Ethnic Origin

There are no enrollment restrictions based on race or ethnic origin.

Inclusion Criteria

Patients will be screened for eligibility using the following criteria. All study subjects must meet the following inclusion criteria:

- Patients undergoing an arthroscopic shoulder procedure (rotator cuff repair, decompression, labrum repair)
- Patients ages 18-75, inclusive

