Information to be recorded pre-operatively includes age, sex, height, weight, BMI, and American Society of Anesthesiology (ASA) classification. As well as baseline levels of complete blood count (CBC), chemistry profile, liver enzymes, gamma glutamate transferase (GGT), electrocardiogram, urine analysis, 12-panel urine drug test, and a urine pregnancy test.

Intra-operative information will also be recorded, including operative time, procedure, number of anchors, and complications. Patients will subsequently be stratified in different subgroups based on the procedure performed.

Pain severity scores at rest will be assessed by use of a visual analog scale (VAS; 0 = no pain, 10 = worst pain imaginable) at 6, 24, and 48 hours as well as 7 days and 14 days after surgery.

Patients will record their satisfaction with their management, on a 0-10 scale, 24 hours, 2 days and 7 days, and 14 days after surgery.

Additionally, any nausea experienced by the patients will be recorded by use of a VAS (0 = no nausea, 10 = worst nausea imaginable) at 2 days, 7 days and 14 days after surgery.

Percocet consumption will be recorded at 24 hours, 2 days and 7 days, and 14 days after surgery. Additionally, subjects will be asked to record the dates and times of CBD consumption.

Liver function tests, consisting of the standard hepatic panel, and including serum transaminase and bilirubin levels will be administered for study purposes on Day 7 and Day 14 after surgery.

Incidence of CBD-related side effects will be noted. Time to discharge from the post-anesthesia care unit (PACU) and time to discharge from the hospital will be recorded. Patients will be in the study a duration of 14 days and will be asked to fill out one online survey at the 1-year mark to determine the long-term effects that may be associated with using CBD.

In order to maintain the blinding, all data, including pain severity scores, side effects, opioid and CBD consumption, will be collected by the resident physician or physician assistant. However, if needed, in the event of an emergency or SAE, the unblinded surgeon responsible for randomization will be able to confirm whether a subject has been assigned to receive CBD or placebo.

| Study Time Points | |
|------------------------|---|

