| Day 0 - Day of Surgery | Baseline suicidality assessment (C-SSRS), Record Pain (6hrs and 24 hrs), Record clinical data during surgery and post op including time to discharge from PACU and time to discharge from the hospital, monitor for AEs |
| Day 1 | Record Pain, Opioid consumption, CBD consumption, Satisfaction, monitor for AEs |

The use of cannabidiol (CBD) in pain reduction and opioid use after shoulder arthroscopy. A Double-Blind, Randomized Control Study

Version 06/28/2022

| | |
|-----------------------------------|--|
| Day 2 | Record Pain, Opioid consumption, CBD consumption, Satisfaction, Nausea, monitor for AEs |
| Day 7 - Standard of Care Visit 1 | Record Pain, Opioid consumption, CBD consumption, Satisfaction, Nausea, Liver Function Tests - Non-standard of care, C-SSRS, Drug accountability, monitor for AEs |
| Day 14 - Standard of Care Visit 2 | Record Pain, Opioid consumption, CBD consumption, Satisfaction, Nausea, monitor for AEs Liver Function Tests - Non-standard of care, C-SSRS, Drug accountability and review of completed subject diary, monitor for AEs |
| Month 12 – Post-Trial Survey | Record Pain; Complete ASES, KJOC Shoulder, and SANE assessment |

Data Analysis and Statistical Plan

Our power analysis was based on the literature of post-operative pain control following shoulder arthroscopy. Under the assumption of a VAS of 3 and 1.8 for the control and CBD respectively, with a SD of 2: Group sample sizes of 45 in each group would achieve 80% power to reject the null hypothesis of equal means when the population mean difference between Control and CBD is $\mu_1 - \mu_2 = 3.0 - 1.8 = 1.2$ with a standard deviation for both groups of 2.0 at a significance level (alpha) of 0.05 using a two-sided two-sample equal-variance t-test. Thus, to allow for a 5% drop-out at 14-day follow-up, 100 patients would be required to enroll.

For descriptive statistics, categorical values will be described by percentages, and continuous variables will be described by means with standard deviations. To compare primary and secondary outcomes, a T-Test will be performed, with a p-value of 0.05 set to determine statistical significance. Testing will be performed to determine whether sample distribution is normal; if not, non-parametric testing will be performed.

Analysis of the Primary Efficacy Endpoint(s)

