To compare primary outcomes (VAS score), a T-Test test will be performed, with a p-value of 0.05 set to determine statistical significance. Testing will be performed to determine whether sample distribution is normal; if not, non-parametric testing will be performed. Patients who do not complete at least 80% of follow-up visits will be considered lost to follow-up and will not be included in the analysis.

Analysis of the Secondary Endpoint(s)

To compare secondary outcomes (opioid use, satisfaction), complication rates), a T-Test will be performed, with a p-value of 0.05 set to determine statistical significance. For categorical variables, a Fisher's exact test will be performed. Testing will be performed to determine whether sample distribution is normal; if not, non-parametric testing will be performed. Patients who do not complete at least 80% of follow-up visits will be considered lost to follow-up and will not be included in the analysis.

Data and Safety Monitoring Plan

Data monitoring will be done by [name], the principal investigator will oversee the conduct of the study. He will review enrollment, accumulated study data, including pain VAS scores, Percocet consumption VAS scores, liver function test results, adverse events, protocol deviations, study compliance and data accuracy quarterly.

He will monitor whether or not:

1. Collection and storage of patient data was performed in a sensitive and secure manner, as defined in the informed consent form and protocol, ensuring information is stored on REDCap.
2. All study activities were conducted with primary emphasis on patient care and wellbeing, ensuring the patients are not in discomfort and have an abnormally high VAS following the surgery.
3. If there were any adverse events, and if so were addressed appropriately and per protocol
4. The risk/benefit to patients has remained the same throughout the course of the study.

The study will be stopped if there are unexpected severe adverse events in more than one patient. Adverse Events (AEs) will be defined as negative reactions to the CBD treatment. We will submit summaries of data and safety monitoring to the IRB annually. De-identified primary and secondary outcome data will be shared by the participating site PI quarterly, and they will notify the host site PI ([name]) upon each enrolled patient.

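### The primary outcome is a pain VAS scored at five times, with no primary time, summary over time or multiplicity rule

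*Combined protocol and SAP*

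**What the plan says.** The file is both protocol and SAP, so the primary comparison should be fixed here. The relevant statements are:

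- **Analysis of the Primary Efficacy Endpoint(s), section III:** "To compare primary outcomes (VAS score), a T-Test test will be performed, with a p-value of 0.05 set to determine statistical significance". The general paragraph under Data Analysis and Statistical Plan repeats the t-test and the 0.05 threshold and adds no time.
- **Primary Objective, section I:** to look for "any differences in post-operative pain between patients receiving CBD after shoulder arthroscopy compared to patients who do not receive it". No time is given.
- **Methods and Procedures, section III:** pain at rest is scored "at 6, 24, and 48 hours as well as 7 days and 14 days after surgery", which is five times.
- **Study Design, section I:** "Patients will be asked on postoperative Day 1, 2, 7, and 14 to rate their pain according to the VAS scale". This is four times, without 6 hours.
- **Study Time Points table, section III:** the 6-hour and 24-hour scores are listed under Day 0, and pain is recorded again on Days 1, 2, 7 and 14. A post-trial Month 12 row reads "Record Pain; Complete ASES, KJOC Shoulder, and SANE assessment".
- **Power paragraph, Data Analysis and Statistical Plan:** "Under the assumption of a VAS of 3 and 1.8 for the control and CBD respectively, with a SD of 2", for 45 per group, 80% power and a two-sided t-test at 0.05. Enrolment is then raised "to allow for a 5% drop-out at 14-day follow-up".

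**The concern.** The wording of the primary analysis fits at least three different plans: one test at an unnamed time, one test of an unnamed summary such as the mean over time, or a separate test at each time. Two analysts could follow the document faithfully, test different times, reach opposite conclusions and both be compliant.

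The times are not interchangeable. All patients have an interscalene block and take study tablets as needed for 14 days, so pain at 6 hours and pain at Day 14 answer different questions.

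Two things are at stake. First, if the time is chosen after results are seen, or if any significant time counts, the 0.05 threshold no longer gives a 5% false-positive rate. Second, the 80% power belongs to one comparison that the plan does not identify, so it cannot be checked against the outcome that will be reported.

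**Working it through.** **1. The plan's own figure.** Inputs from the power paragraph: means 3.0 and 1.8, SD 2, 45 per group, two-sided 0.05.

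- Standardised difference: 1.2 / 2 = 0.6.
- Noncentrality: 0.6 × √(45/2) = 2.846, with 88 degrees of freedom and critical t = 1.987.
- Power from the noncentral t distribution: 80.4%. The stated 80% reproduces.
- At the full 50 per group: noncentrality 0.6 × √(50/2) = 3.0, power 84.4%.

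This is the power of one comparison. If that comparison is named in advance, its false-positive rate is 5%.

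**2. False-positive rate if every time is tested at 0.05 and any one may count.** With no true effect, *k* test statistics and a common correlation ρ between times, with c = 1.96:

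P(at least one significant) = 1 − ∫ φ(u) [Φ((c − √ρ·u)/√(1−ρ)) − Φ((−c − √ρ·u)/√(1−ρ))]^k du

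At ρ = 0 this reduces to 1 − 0.95^k. The documents give no correlations, so every value of ρ is an assumption.

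| Times counted | ρ = 0 | ρ = 0.5 | ρ = 0.7 | ρ = 0.9 |
|---|---|---|---|---|
| 4 (Study Design list) | 18.5% | 15.6% | 13.0% | 9.4% |
| 5 (Methods list) | 22.6% | 18.3% | 14.8% | 10.2% |
| 6 (Methods list plus Month 12) | 26.5% | 20.7% | 16.4% | 10.8% |

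The ρ = 0 column is an unlikely upper bound for repeated scores in the same patient.

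**3. Check with actual t-tests.** Simulating two-sample t-tests with 45 per arm and equal correlation (60,000 trials) gave 18.3%, 14.9% and 10.0% for five times at ρ = 0.5, 0.7 and 0.9, in line with the integral.

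**4. Correlation that falls with distance.** If neighbouring times correlate at 0.5, 0.7 or 0.9 and the correlation shrinks with each further step (ρ^|i−j|), the same simulation gave 20.1%, 17.2% and 11.9% for five times, and 16.6%, 14.5% and 10.5% for four.

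**5. Cost of correcting afterwards.** Bonferroni over five times means 0.05 / 5 = 0.01 each. With the same difference and SD, power at any one time falls to 58.6% at 45 per arm and 64.6% at 50.

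**6. Why the power must be tied to the measure.** If the SD at each time is 2 and correlations are equal, the mean of five scores has SD 2 × √((1 + 4ρ)/5): 1.55, 1.74 or 1.92 at ρ = 0.5, 0.7 or 0.9. The expected difference in that mean may also not be 1.2. One pair of planning values therefore cannot be assumed to fit every candidate measure.

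**The case against.** The best case for the plan is that it intends a single test. The analysis sentence refers to one t-test, the power paragraph uses one pair of means, and the 14-day drop-out allowance points to Day 14. On that reading the error rate is 5% and the inflation above never arises. This has some force: the any-time rule is not written in the plan, and the percentages describe a scenario. But the 14-day phrase only sets an attrition allowance, and a summary over all times would need follow-up to Day 14 just as much. Even if one test was meant, the plan does not say which.

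Four smaller points also deserve an answer:

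- The 10–18% range covers five times and equal correlation only. The four-time list and falling correlations widen it to roughly 9–20%.
- The figures count false positives in either direction, while the stated hypothesis is that CBD reduces pain. False results favouring CBD make up half, about 5–9% for five times, against 2.5% for one test. The relative inflation is the same.
- The Month 12 score is described as post-trial, so leaving it out of the main count is reasonable. Including it raises the rates slightly.
- The 6-hour score is missing only from the Study Design summary. Methods and Procedures and the time-points table both include it, so this is a mismatch to tidy and does not put its collection in serious doubt.

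None of these supplies the missing definition.

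**Conclusion.** The concern holds with high confidence, and the point must be fixed. No primary time, summary measure or multiplicity rule appears anywhere in the document, and no redaction explains the gap. That finding rests on the text alone and needs no assumed numbers.

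The size of the inflation is conditional on testing each time at 0.05 and letting any one count. Under that rule, and at assumed correlations of 0.5 to 0.9, five times give a false-positive rate about two to nearly four times the nominal level (10.2% to 18.3%), or up to 20.1% if correlation falls with distance. With one pre-named comparison the rate is 5%. The planned power then stands, provided the 1.2 difference and SD of 2 apply to that comparison.

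**What to change.** Before unblinding or any by-arm look at VAS, add a dated statement that does the following:

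1. Names one primary comparison at two-sided 0.05: either VAS at one scheduled time, or one summary over the scheduled times (for example the mean, or a single contrast from a repeated-measures model). The choice is the investigators'.
2. States that the 1.2 difference and SD of 2 refer to that measure, or restates the power for it.
3. Labels every other VAS time, including Month 12, as secondary or exploratory.
4. Makes the pain times in Study Design, Methods and Procedures and the Study Time Points table agree, including 6 hours and whether the 24-hour and Day 1 scores are the same record.
5. Records whether the quarterly review of accumulated VAS scores in the Data and Safety Monitoring Plan has been pooled or by arm, since the text does not say and this bears on whether the choice was made blind.

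The cost is a few sentences, with no extra data or patients, plus a fresh power justification if the planning values do not suit the chosen measure. There are two real downsides. A difference at another time can no longer be claimed as the primary result, and a mean over time loses power if the effect is short-lived.

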Additionally, it is the hope of the research team that results of this study will benefit future patients and their physicians by providing more information regarding the use of CBD after surgery. This will allow for a more open and informed dialogue, and possibly a change standard of care treatment.

Drug Shipment, Storage, Dispensing, Accountability, and Destruction: The CBD and matching placebo ODTs will be shipped to the NYU Langone Health Research Pharmacy in bottles labeled CBD or Placebo 25mg ODT with the subject #, date of dispensing and # of ODTs. Subjects will be dispensed enough 25mg ODTs for a maximum dose of every 4-6 hours for 14 days (subjects weighing over 80kg will be dispensed twice the amount of ODTs to account for 2 ODTs per dose (a total of 50mg CBD or placebo per dose). Subjects will be reminded that they should take the CBD or placebo ODT orally, every 4-6 hours, as needed for 14 days. The dates and times the ODT is taken are to be recorded in the subject's diary. Subjects will need to bring the drug with them (including empty and unused bottles) to the site for their Day 7 and Day 14 visits for accountability. Any remaining drug will be collected at Day 14 and destroyed per NYULH Research Pharmacy SOP.

V. INVESTIGATOR'S QUALIFICATIONS AND EXPERIENCE

The CV, medical license, and human subjects' tutorial completion report are attached for all investigators who are participating in this study. All research personnel have medical research experience and are qualified to participate in this quality study. Most importantly, staff have been properly educated and certified with CITI training to conduct research in a matter that will maintain full patient confidentiality. The research coordinator for this study is trained in GCP

principles and practices and will be responsible for compliance with GCP guidelines for all study investigators and research assistants.

VI. SUBJECT IDENTIFICATION, RECRUITMENT AND CONSENT/ASSENT

Method of Subject Identification and Recruitment

Appropriate patients, who meet all of the inclusion criteria and none of the exclusion criteria, who require a shoulder arthroscopy, will be identified from the clinical offices of the investigator surgeons.

Process of Consent

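### The 80% attendance rule drops randomised patients, with scores they have already given, from the primary and secondary analyses; no all-randomised analysis is planned and the counted visits are undefined

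*Combined protocol and SAP*

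**What the plan says.** Under Analysis of the Primary Efficacy Endpoint(s) the rule reads: "Patients who do not complete at least 80% of follow-up visits will be considered lost to follow-up and will not be included" in the analysis. The same sentence closes Analysis of the Secondary Endpoint(s), which begins "To compare secondary outcomes (opioid use, satisfaction), complication rates), a T-Test will be performed". No section describes an intention-to-treat, full or all-randomised set, a method for missing data, or a sensitivity analysis.

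The contacts that the rule counts are not defined. The documents offer three lists:

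- **Two visits.** The Study Time Points table uses the word visit only for Days 7 and 14, for example "Day 7 - Standard of Care Visit 1". The drug accountability section has subjects bring their drug "to the site for their Day 7 and Day 14 visits for accountability".
- **Four pain days.** Study Design: "Patients will be asked on postoperative Day 1, 2, 7, and 14 to rate their pain according to the VAS scale".
- **Five pain times.** Methods and Procedures records VAS "at 6, 24, and 48 hours as well as 7 days and 14 days after surgery".

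The 12-month survey is labelled post-trial, and Methods and Procedures states "Patients will be in the study a duration of 14 days", so I do not count it.

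Methods and Procedures places randomisation after consent and chart review, before any follow-up. Subject withdrawal criteria and Protection against Risks both remove patients with raised liver tests from the study.

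**The concern.** Attendance is observed after randomisation and may depend on pain, side effects or removal for a laboratory result. A comparison restricted to patients who attended enough visits is no longer the randomised comparison. Because it is the only one specified, nothing planned would show whether the exclusions changed the answer.

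The rule also goes beyond ordinary missing data. A patient who gave a VAS score at the analysed time but missed another contact is dropped with that score. And because the counted contacts are not listed, the analysed set is not fixed in advance: a patient who misses only Day 2 is kept if two visits are counted and dropped if four days are counted.

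**Working it through.** **Inputs from Data Analysis and Statistical Plan and Number of Subjects:** difference 3.0 − 1.8 = 1.2; SD 2.0; two-sided alpha 0.05; equal-variance t-test; 45 per group for 80% power; 5% drop-out; 50 per arm enrolled.

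**Step 1: the plan's own figure.** Noncentral-t power with noncentrality δ / (σ√(1/n1 + 1/n2)). At 45 per arm this is 1.2 / (2√(2/45)) = 2.85, giving 80.4%. The stated 80% reproduces.

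**Step 2: what 80% requires.** Contacts needed = 0.8 × V, rounded up. Share excluded if each contact is missed independently with probability 5% (assumed):

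| Reading | Needed | Excluded |
|---|---|---|
| Days 7, 14 | 2 of 2 | 1 − 0.95² = 9.75% |
| Days 1, 2, 7, 14 | 4 of 4 | 1 − 0.95⁴ = 18.5% |
| 6, 24, 48 h, Days 7, 14 | 4 of 5 | 1 − 0.95⁵ − 5(0.05)(0.95⁴) = 2.3% |

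**Step 3: bias.** Let f be the share excluded in an arm and g the mean VAS of excluded minus retained patients in that arm. The retained mean lies f × g below the full arm mean, so the bias towards CBD is f_CBD × g_CBD − f_placebo × g_placebo. It is zero when rates and gaps match. Assume g = 2 in both arms, SD 2, 50 randomised per arm and no true effect. Type I error is by normal approximation, with SE = 2√(1/n1 + 1/n2).

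- 7% CBD versus 3% placebo (average 5%): bias (0.07 − 0.03) × 2 = 0.08. Expected n 46.5 and 48.5, SE 0.410, type I error 5.4%.
- 20% versus 5%: bias (0.20 − 0.05) × 2 = 0.30. Expected n 40 and 47.5, SE 0.429, type I error 10.8%.
- Arms reversed: the same bias against CBD. A true 1.2 appears as 1.12 (power 77.0%) or 0.90 (power 54.5%).

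**Step 4: rule or missing data?** A simulation of 8,000 runs assumed no true effect, within-patient correlation 0.5, and a chance of missing Day 14 that depends on the recorded Day 7 score, calibrated to a 2-point gap. At 20% versus 5% missing, the Day 7 comparison in the 80% set has bias 0.30 and type I error 11.4%. Using every recorded Day 7 score gives bias under 0.01 in size and 5.4%. At Day 14 the 80% set has bias 0.14, but there the excluded patients have no Day 14 score to discard. At 7% versus 3% the 80% set has bias 0.08 (Day 7) and 0.04 (Day 14).

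**Step 5: power without the rule.**

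- 50 per arm, effect 1.2: 84.4%.
- 45 per arm (10% missing), effect 1.2: 80.4%.
- 45 per arm, with 5% of the CBD arm gaining nothing (assumed), so effect 0.95 × 1.2 = 1.14: 76.2%.

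**The case against.** **Small at the planned loss.** At 5% overall the illustrated bias is 0.08, about 7% of the 1.2 effect (0.08 / 1.2), and equal 5% exclusion leaves 82.5% power (47.5 per arm). The larger figures need 20% versus 5% exclusion and a gap of one full SD; nothing in the documents supports either. This stands as a limit on size. It does not rescue the rule: on two of the three readings a single miss excludes, so exclusions can exceed the 5% allowance.

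**Day 14.** If the analysed score is Day 14, a patient lost before then has nothing to discard, and the problem is ordinary missing data. This stands. The plan names no single VAS time as primary, so the earlier times, where the rule itself does the harm, are not ruled out.

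**The term is not wholly open.** Only Days 7 and 14 are called visits, and Protection against Risks mentions follow-up visits before placing the suicidality assessment at baseline, Day 7 and Day 14. That favours two visits. An 80% threshold is odd for two visits, though, and no definition is given.

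Three stronger readings are tempting, and the documents do not support them:

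- *That the rule favours CBD.* Direction cannot be derived.
- *That it hides adverse events or liver results.* The analysis paragraphs do not name these as outcomes. Methods and Procedures uses complications for intra-operative data ("including operative time, procedure, number of anchors, and complications"), and Adverse Event Reporting requires all events to be documented.
- *That liver-test removal always causes exclusion.* This holds only if contacts then stop, which is not stated. If they do, removal on Day 2 leaves 0 of 2, 2 of 4 or 3 of 5 contacts, and removal on Day 7 leaves 1 of 2 or 3 of 4; all fall short of 80%. On the five-time reading, removal on Day 7 leaves 4 of 5 and the patient stays in. Hepatic toxicity is listed as rare, and abnormal liver tests exclude at entry.

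**Conclusion.** The rule is wrong as written and should be changed before the data are analysed. Followed exactly, the plan replaces the randomised comparison with one selected on later attendance, discards recorded scores, and does not fix who is analysed. That conclusion rests on the text alone.

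The size of the harm does not: every bias figure depends on assumed exclusion rates and an assumed 2-point gap. It runs from nothing, through a small distortion at the plan's own loss rate, to a quarter of the planned effect (0.30 / 1.2) only under heavier and unequal exclusion. The loss of power from the rule is a lesser matter.

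**What to change.** 1. Delete the 80% sentence from both endpoint paragraphs.
2. Make the primary analysis all randomised patients, in their assigned arm, with an available VAS score at the analysed time point, using the planned t-test.
3. Report missing scores and reasons by arm.
4. Add a missing-data sensitivity analysis: for example a repeated-measures model over the scheduled scores, or multiple imputation with shifted values.
5. Keep the 80% set only as a sensitivity analysis, with the counted contacts listed.

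**Cost.** This is a change of SAP wording, with no new contacts. The price is possible dilution by patients who stopped the ODTs. The enrolled number keeps 80% power with 10% missing only if the full 1.2 effect holds (Step 5), so it cannot be promised that no extra patients are needed. A repeated-measures model does not correct for missingness driven by pain that was never recorded, which is why item 3 is needed.

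**Separately, to be reconciled.** Subject withdrawal criteria and Protection against Risks agree on removal for liver tests. They differ on whether raised transaminase and bilirubin are alternatives or both required, and on the days named. Both refer to a Day 2 liver test that Methods and Procedures and the Study Time Points table do not schedule. The documents should also say whether removal ends data collection. No clinical rule is proposed here.
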